8.1.4 Sub-study

For all efficacy variable derivations, the date of first dose of ^{177}Lu -PSMA-617+BSC/BSoc, as defined in Section 5, will be used as the reference date instead of the date of randomization. All efficacy derivations will be based on local investigator assessment; no central assessments will be performed.

8.2 Efficacy Analyses

The primary analysis of rPFS per independent central review will be based on the PFS-FAS while the primary analysis of OS will be based on the FAS. The analyses of the secondary efficacy endpoints will be performed on the PFS-FAS, defined in Section 5.3, except for soft tissue response (ORR and DCR) as measured by RECIST 1.1, for which the primary analysis will be performed on the Response Evaluable Efficacy Analysis Set. The randomization stratification factors from the IRT system will be used for all efficacy analyses unless otherwise specified.

All data summaries will be presented by treatment arm.

8.2.1 Primary Efficacy Analyses

The alternate primary efficacy endpoints are OS and rPFS (defined in Section 8.1.1). For the primary analysis of rPFS with an interim analysis of OS, and final analysis of OS (see Section 4), the analyses described below will be done using 1-sided tests of treatment differences. If the formal interim OS analysis is met at the pre-specified alpha level, the final OS will only be presented descriptively without statistical inference at the nominal alpha level specified in Section 3.4. However, if the interim analysis of OS is not performed, the alpha level applicable to the OS analysis will depend on the final rPFS results as described in Section 4.

Overall Survival

The null hypothesis for OS, as stated in Section 3.4, will be tested at a one-sided level of significance. The primary analysis is to test the null hypothesis and compare the two treatment arms using a stratified log-rank test stratifying for the randomization stratification factors. The alternate primary efficacy variable, OS, will be analyzed at the interim analysis and final analysis as defined in Section 4.

The primary analysis of OS at the interim and final analysis will be based on the FAS population. The OS distribution will be estimated using the Kaplan-Meier method, and Kaplan-Meier curves (including number at risk and confidence limits), median, 25th percentile, and 75th percentile and associated 99.8% confidence intervals at the interim analysis and 95% or 96% confidence intervals at the final analysis (depending on the earlier rPFS and interim OS results, Section 3.4 or depending on the final rPFS results if the interim OS analysis is not performed, Section 4) will be presented for each treatment arm. The OS Kaplan-Meier estimate along with 99.8% confidence intervals at the interim analysis and 95% or 96% confidence intervals at the final analysis, will be presented at different time points (e.g. 6, 12, and 18 months) for each treatment arm. The one-sided p-value from the log-rank test will be presented at the interim and final analysis.

A supportive analysis will be performed in terms of a stratified Cox regression model with a single covariate for randomized treatment arm, stratifying again for the randomization stratification factors. The hazard ratio for OS will be calculated, along with its 99.8% confidence interval at the interim analysis and its 95% or 96% confidence interval at the final analysis, from the stratified Cox model. The HR and CI from this model will be used as an adjunct to the primary stratified log-rank test p-value to provide the quantification of the treatment effect on OS.

The following data will be provided for the analysis of OS:

- Median follow-up (months) with 95% CI using the Kaplan-Meier method, censoring for deaths, and range
- Kaplan-Meier curves with 99.8% confidence limits at interim and 95% or 96% confidence limits at final and number at risk
- Number (%) events and censored, reason censored (alive, lost to follow-up, withdrew consent)
- Kaplan-Meier median, 25th percentile, and 75th percentile with 99.8% CIs at interim and 95% or 96% CIs at final
- Overall Survival rates and standard errors at 6 months, 12 months, and 18 months with 99.8% CIs at interim and 95% or 96% CIs at final
- Cox regression HR (active: control) with 99.8% CI at interim and 95% or 96% CI at final
- Log-rank test 1-sided p-value

Visual checks of the proportional hazard assumption will be performed based on the Plots (SURVIVAL LOGSURV LOGLOGS) generated by LIFETEST procedure in SAS. No formal analysis will be generated. If the proportional hazard assumption doesn't hold, additional methods may be explored to assess the treatment effect. Further details will be provided in a separate post-hoc analysis plan.

Radiographic Progression-Free Survival

The null hypothesis for rPFS per independent central review, as stated in Section 3.4, will be tested at a one-sided level of significance. The primary analysis is to test the null hypothesis and compare the two treatment arms using a stratified log-rank test stratifying for the randomization stratification factors. The alternate primary efficacy variable, rPFS, will be analyzed when 364 rPFS events have occurred (Section 4).

The primary analysis of rPFS will be based on the PFS-FAS population. The rPFS distribution will be estimated using the Kaplan-Meier method, and Kaplan-Meier curves (including number at risk and confidence limits), median, 25th percentile, and 75th percentile and associated 99.2% confidence intervals will be presented for each treatment arm. The rPFS Kaplan-Meier estimate along with 99.2% confidence intervals will be presented at different time points (e.g. 3, 6, and 12 months) for each treatment arm. The one-sided p-value from the log-rank test will be presented.

A supportive analysis will be performed in terms of a stratified Cox regression model with a single covariate for randomized treatment arm, stratifying again for the randomization stratification factors. The hazard ratio for rPFS will be calculated, along with its 99.2% confidence interval, from the stratified Cox model. The HR and CI from this model will be used as an adjunct to the primary stratified log-rank test p-value to provide the quantification of the treatment effect on rPFS.

The following data will be provided for the analysis of rPFS:

- Median follow-up (months) with 95% CI using the Kaplan-Meier method, censoring for radiographic progressions or deaths, and range
- Kaplan-Meier curves with 99.2% confidence limits and number at risk

- Number (%) events and censored, reason censored (ongoing without event, event documented after 2 or more missed tumor assessments, adequate assessment not available)
- Kaplan-Meier median, 25th percentile, and 75th percentile with 99.2% CIs
- rPFS rates and standard errors at 3 months, 6 months, and 12 months with 99.2% CIs
- Cox regression HR (active: control) with 99.2% CI
- Log-rank test 1-sided p-value

Visual checks of the proportional hazard assumption will be performed based on the Plots (SURVIVAL LOGSURV LOGLOGS) generated by LIFETEST procedure in SAS. No formal analysis will be generated. If the proportional hazard assumption doesn't hold, additional methods may be explored to assess the treatment effect. Further details will be provided in a separate post-hoc analysis plan.

Sensitivity and supportive analyses for rPFS:

For all sensitivity and supportive analyses of the alternate primary endpoints, rPFS and OS, the nominal one-sided p-value will be provided without any statistical inference.

First Sensitivity analysis of rPFS: This sensitivity analysis is the same as the primary rPFS analysis (Section 8.1.1) except with additional rPFS events as follows:

- Includes events regardless of intervening missed assessments.
- Bone PDs are indicated by one of the following per PCWG3 guidelines:
 - Rule 1 (Progression at week 8 and confirmed at week 16): same as Rule 1 described in Section 8.1.1.
 - Modified Rule 2 (Progression at week 16 or later without confirmation): PD can still only occur at the second post treatment scan or later. The date of bone PD is the date when there are at least two new lesions relative to the first post-treatment scan without confirmation.
- Includes all radiographic PD and deaths captured in the study, including scans not centrally read that are captured on the LTFU CRF page.

This sensitivity analysis will use the PFS-FAS population and will compare the two treatment arms using the same analysis conventions described in Section 8.2.1.

Second Sensitivity analysis: This sensitivity analysis is the same as the primary rPFS analysis except with additional censoring as follows:

- Deaths occurring after start of a new anti-cancer therapy will be censored at start date of new therapy.

This sensitivity analysis will use the PFS-FAS population and will compare the two treatment arms using the same analysis conventions described in Section 8.2.1.

Third Sensitivity analysis: This sensitivity analysis is the same as the primary rPFS analysis except rPFS will be defined from the date of first dose of randomized treatment. This sensitivity analysis will use the PFS-FAS population and will compare the two treatment arms using the same analysis conventions described in Section 8.2.1.

Fourth Sensitivity analysis: This sensitivity analysis is the same as the primary rPFS analysis except using local investigator assessments. This sensitivity analysis will use the PFS-FAS population and will compare the two treatment arms using the same analysis conventions described in Section 8.2.1.

Sensitivity analyses to assess the impact of COVID-19:

The impact of missing PCWG3 (bone scans) and/or RECIST assessments on the primary rPFS analysis caused by COVID-19 will be evaluated by the existing first sensitivity analysis.

The following analyses of rPFS will be used to estimate the treatment effect in the absence of the COVID-19 virus:

- Analysis as per the primary rPFS analysis but censoring COVID-19 related deaths at the last adequate assessment prior to the death.
- An analysis as per the 'first sensitivity analysis' but censoring COVID-19 related deaths at the date of death.

For the analyses above, the patients with COVID-19 related deaths will be determined in a blinded fashion by clinical review of the data and will be documented prior to database lock.

The same analyses conventions used for the primary analyses of rPFS, as described in section 8.2.1, will be performed (without p-values).

Supportive analyses of rPFS:

rPFS will be derived in all patients randomized (FAS population) using the same conventions as described in Section 8.1.1 but will consider patients randomized before March 5, 2019 who withdrew consent from the study (i.e. no further data on radiographic progression is available) as (1) censored at time of withdrawal and (2) a rPFS event at the time of withdrawal.

The following data will be summarized using the FAS:

- (1): Number (%) rPFS events (radiographic PD, deaths) and censored, reason censored (ongoing without event, withdrew consent, event documented with two or more missed tumor assessments, adequate assessment not available)
- (2): Number (%) rPFS events (radiographic PD, deaths, withdrew consent) and censored, reason censored (ongoing without event, withdrew consent, event documented with two or more missed tumor assessments, adequate assessment not available)

Missing tumor assessments: The number of patients with at least one missing/not evaluable tumor assessment (TA) based on independent central review will be presented together with the following breakdown categories: number of patients with 1, 2, 3, 4, 5, >5 missing/not evaluable TAs. The purpose of this analysis is to gain an insight as to whether the TAs have been carried out in accordance with the protocol and to understand if any meaningful discrepancies exist between the pattern of missing assessments by treatment arms. Timing of all tumor assessments will be depicted graphically and displayed by treatment arm.

Since the planned tumor assessments are every 8 weeks in the first 24 weeks from C1D1 and every 12 weeks thereafter, the following time windows (in weeks) will be constructed for each patient from the date of randomization: (note the open parenthesis such as (12, 20] indicates that week 12 doesn't belong to this interval and week 12+1 day belongs to that interval)

- Until ~24 weeks post randomization [0, 12], (12, 20], (20, 28]
- After ~24 weeks post randomization (28, 42], (42, 54], (54, 66], ...

where '0' is the patient's date of randomization. Every time-window (with the exception of the initial, broader one) is centered at the scheduled time of a TA, i.e., around week 16, week 24 for second and third window respectively, etc. A patient will be considered 'at risk' of missing a TA for any one of these time-windows if the patient either:

- is 'on study' for at least the first 4 weeks of the time-window for the first 24 weeks (8 weeks for the first time window), or at least the first 6 weeks of time-window thereafter, i.e., if the patient is ongoing at the time of the scheduled TA, or
- discontinued treatment due to documented disease progression within the specific time window.

For example, if a patient discontinued due to documented disease progression during Week 24, then the patient would have been 'at risk' of a missing/not evaluable TA for the [20, 28] week time window.

For the purpose of this analysis, 'not evaluable' TAs (i.e., evaluations with an overall tumor response of 'not evaluable' per central independent review) will be considered to be missing. However, a clear distinction between 'truly missing' and 'present but not evaluable' needs to be made in the derived dataset to allow for both a combined analysis, i.e. missing and not evaluable treated the same, and separate analyses.

TAs performed after a documented radiographic disease progression per independent central review will not be considered. In other words, the final time-window for which a patient would be at risk of a missing/not evaluable scan would be that during which the documented radiographic progression occurred.

For patients without documented radiographic progression per independent central review, all TAs are considered up to the earliest of the following dates: death, the analysis cut-off, discontinuation due to disease progression, withdrawal of consent or loss to follow-up.

Concordance between local and central review: A summary on censoring reasons will be produced for rPFS by investigator and central radiology. The censoring patterns will be compared between investigator and central review. A comparison of rPFS event type/censor between local radiology review and central radiology review will be provided using the PFS-FAS population.

Sensitivity and supplementary analyses for OS:

Supplementary analysis of OS:

A supplementary descriptive analysis of OS will be performed using the PFS-FAS population. This analysis will use the same analysis conventions described in Section 8.2.1 but will be descriptive with the nominal p-value presented.

Sensitivity analyses to assess the impact of COVID-19:

The following analyses of OS will be used to estimate the treatment effect in the absence of the COVID-19 virus:

- Analysis as per the primary OS analysis but censoring COVID-19 related deaths at the date of death.

For the analyses above, the patients with COVID-19 related deaths will be determined in a blinded fashion by clinical review of the data and will be documented prior to database lock.

The same analyses conventions used for the primary analyses of OS, as described in section 8.2.1, will be performed (without p-values).

Subgroup analyses for rPFS and OS:

If either of the primary efficacy analyses of the alternate endpoints are statistically significant, the alternate primary endpoints of rPFS and/or OS will be summarized for subgroups, as specified in Section 5.4.1. Subgroup analyses of rPFS and OS will be presented graphically using forest plots.

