3.4 Sample Size Justification

The sample size was determined based on the alternate primary endpoints of rPFS and overall survival. Planned enrollment for this study is approximately 814 subjects.

Under the null hypothesis for survival, median overall survival is assumed to be 10 months on ¹⁷⁷Lu-PSMA-617 and best supportive/best standard of care (active) for a hazard ratio (HR) of 1.00. Under the alternative hypothesis, median overall survival on active is assumed to be 13.7 months for a HR of 0.7306.

Under the null hypothesis for rPFS, median rPFS is assumed to be 4 months on ¹⁷⁷Lu-PSMA-617 and best supportive/best standard of care (active) for a HR of 1.00. Under the alternative hypothesis, median rPFS on active is assumed to be 6 months for a HR of 0.67.

Based on a non-linear patient accrual profile over 14 months, a total of 814 patients randomized and followed on an ITT basis for a minimum of 13 months is expected to yield

508 deaths. This number of events provides at least 90% power to test the hypothesis that the HR for OS is 0.7306 or better with a 1-sided alpha level of at least 0.020.

For rPFS, a total of approximately 557/814 patients are expected to be randomized on or after 5 March 2019, these being the patients to be included in the primary analysis of rPFS; with a minimum of approximately 6 months follow-up, these patients are expected to yield 364 rPFS events which will be sufficient to provide 84% power to test the hypothesis that the HR of rPFS is 0.67 or better with a 1-sided alpha level of 0.004. At the time of this rPFS analysis, 341 deaths are expected amongst all randomized patients. These interim OS data will be analyzed with a 1-sided alpha level of 0.001. Central independent assessments will be used to determine rPFS events.

The alpha level applicable to OS in the final analysis will depend upon the earlier rPFS and interim OS results:

- if $p < 0.004$ 1-sided is achieved for rPFS and $p < 0.001$ 1-sided is achieved for interim OS, then the alpha level for the final analysis of OS will be raised to 0.025 1-sided.
- if $p < 0.004$ 1-sided is achieved for rPFS but $p < 0.001$ 1-sided is not achieved for interim OS, then the alpha level for the final analysis of OS will be 0.024 1-sided.
- if $p < 0.004$ 1-sided is not achieved for rPFS but $p < 0.001$ 1-sided is achieved for interim OS, then the alpha level for the final analysis of OS will be raised to 0.021 1-sided.

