- if $p < 0.004$ 1-sided is not achieved for rPFS and $p < 0.001$ 1-sided is not achieved for interim OS, then the alpha level for the final analysis of OS will remain at 0.020 1-sided.

This design provides at least 90% power for OS and 84% power for rPFS; with an overall Type I error rate ≤ 0.025 1-sided.

The observed HRs that will meet $p < 0.004$ for rPFS and the interim analysis of OS are 0.745 and 0.701 respectively; and the observed HR that will meet $p < 0.020$ to $p < 0.025$ in the final analysis of OS are 0.824 to 0.823.

4. Planned Analyses

The analyses of the alternate primary endpoints, rPFS and OS, are event driven. The formal planned analysis of rPFS is when 364 rPFS events have been observed in patients randomized on or after 5 March 2019 with an interim analysis of OS at the time of the rPFS analysis using all patients randomized since trial commencement (see Section 5.3.1 for Efficacy Populations). A final analysis of OS, using all patients randomized, will take place when 508 deaths have been observed.

The statistical design of the study is such that, to be declared positive, the study would be required to reach statistical significance on either the primary analysis of rPFS or OS at the respective allocated alpha level; it is not required to meet both rPFS and OS to be declared a statistically positive study.

Note, this applies to OS assessed at either the interim or the final analysis, i.e. for the study to be declared statistically positive requires rPFS to meet its allocated alpha level or OS to meet its allocated alpha level at either (i) the formal OS interim analysis (conducted at the time of the rPFS analysis) or (ii) at the final OS analysis with 508 deaths.

The alpha level applicable to OS in the final analysis will depend upon the earlier rPFS and interim OS results as described in Section 3.4. If the formal interim OS analysis is met at the pre-specified alpha level, the final OS will only be presented descriptively without statistical inference at the nominal alpha level. However, if the formal interim OS analysis is not performed, the alpha level applicable to the OS analysis will depend on the final rPFS results as follows:

- if $p < 0.004$ 1-sided is achieved for rPFS, then the alpha level for the final analysis of OS will be raised to 0.025 1-sided.
- if $p < 0.004$ 1-sided is not achieved for rPFS, then the alpha level for the final analysis of OS will be 0.021 1-sided.

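### SAP 8.2.1 offers only 95% or 96% intervals at final OS, so two of the four alpha levels at which final OS can be tested (0.024 and 0.021) have no matching interval level

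*SAP*

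**What the plan says.** **Interval levels at final OS.** SAP 8.2.1 gives "95% or 96% confidence intervals at the final analysis" for the Kaplan-Meier quantiles and time-point survival estimates in each arm. It adds that the level depends on the earlier rPFS and interim OS results, or on rPFS alone if the interim OS analysis is not performed. The list of OS outputs in the same section repeats the choice for the treatment comparison: "Cox regression HR (active: control) with 99.8% CI at interim and 95% or 96% CI at final".

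**Role of the interval.** The primary OS analysis is a one-sided stratified log-rank test. Of the Cox model, 8.2.1 says: "The HR and CI from this model will be used as an adjunct to the primary stratified log-rank test p-value".

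**Alpha at final OS.** Four cases lead to a formal test:

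- Interim OS not met, rPFS met (Section 3.4): "then the alpha level for the final analysis of OS will be 0.024 1-sided".
- Interim OS not met, rPFS not met (Section 3.4): "then the alpha level for the final analysis of OS will remain at 0.020 1-sided".
- Interim OS not performed, rPFS met (Section 4): "then the alpha level for the final analysis of OS will be raised to 0.025 1-sided".
- Interim OS not performed, rPFS not met (Section 4): "then the alpha level for the final analysis of OS will be 0.021 1-sided".

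If interim OS is met there is no further test. Section 4 states: "If the formal interim OS analysis is met at the pre-specified alpha level, the final OS will only be presented descriptively". Footnote 1 to the first table in 8.2.2 then sets a 95% interval for that descriptive result.

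**Levels elsewhere.** In 8.2.1, interim OS (alpha 0.001) has 99.8% intervals and rPFS (alpha 0.004) has 99.2%. The tables in 8.2.2 pair a final OS result at 0.024 with 95.2%, at 0.020 with 96%, at 0.025 with 95% and at 0.021 with 95.8% for the key secondary endpoints.

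**The concern.** The other formal intervals in 8.2.1 follow one rule: level = 1 − 2 × one-sided alpha. Making the final OS level depend on the earlier results points to the same intention. Two whole-number levels cannot cover four alphas, and 95% and 96% match only 0.025 and 0.020.

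Rounding is not a stated explanation. The same section carries one decimal for 99.8% and 99.2%, and 8.2.2 prints 95.2% and 95.8% for these very scenarios.

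Two things are at stake. The programmer has to choose a level that the plan does not assign. And a result near the boundary could be reported with a hazard-ratio interval that appears to disagree with the p-value beside it. In the 0.024 case, OS would also carry a different level from the key secondary endpoints whose testing depends on it.

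**Working it through.** **Inputs.** 508 deaths at final OS and a design hazard ratio of 0.7306 with at least 90% power at alpha 0.020 (SAP 3.4); 2:1 allocation (SAP 3.2); the four alphas above.

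**Step 1: reproduce the plan's figures.** With 2:1 allocation the information for log HR is 508 × (2/3) × (1/3) = 112.89, with square root 10.625.

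- Power at alpha 0.020: Φ(−ln 0.7306 × 10.625 − 2.0537) = Φ(3.335 − 2.054) = 0.900. This agrees with SAP 3.4.
- Critical HR at alpha 0.020: exp(−2.0537/10.625) = 0.824. This also agrees.
- SAP 3.4 prints 0.823 as the other end of the range, for alpha 0.025. The same formula gives 0.8315, and a larger alpha must give a larger critical HR. That is a separate matter and does not affect this point.

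**Step 2: matching level and critical HR at each alpha.** Level = 1 − 2α; critical HR = exp(−z/10.625).

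| Tested case | α (1-sided) | z | Matching level | Critical HR | In 8.2.1? |
|---|---|---|---|---|---|
| Interim not met, rPFS not met | 0.020 | 2.054 | 96.0% | 0.8242 | yes |
| Interim not performed, rPFS not met | 0.021 | 2.034 | 95.8% | 0.8258 | no |
| Interim not met, rPFS met | 0.024 | 1.977 | 95.2% | 0.8302 | no |
| Interim not performed, rPFS met | 0.025 | 1.960 | 95.0% | 0.8315 | yes |

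**Step 3: size of the mismatch.** The SAP does not assign a level to 0.024 or 0.021, so both pairings are shown.

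| α | Level used | Change in width on the log scale | Range of p where interval and test disagree | HR range | What is seen |
|---|---|---|---|---|---|
| 0.024 | 95% (nearest) | 1.960/1.977: 0.9% too narrow | 0.024–0.025 | 0.8302–0.8315 | test fails, interval excludes 1 |
| 0.021 | 96% (nearest) | 2.054/2.034: 1.0% too wide | 0.020–0.021 | 0.8242–0.8258 | test passes, interval includes 1 |
| 0.024 | 96% | 2.054/1.977: 3.9% too wide | 0.020–0.024 | 0.8242–0.8302 | test passes, interval includes 1 |
| 0.021 | 95% | 1.960/2.034: 3.6% too narrow | 0.021–0.025 | 0.8258–0.8315 | test fails, interval excludes 1 |

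**Step 4: examples, nearest pairing.** Upper limit = HR × exp(z/10.625).

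- p = 0.0245 gives HR 0.831. The upper limit is 0.9992 at 95% and 1.0008 at 95.2%.
- p = 0.0205 gives HR 0.825. The upper limit is 1.0010 at 96% and 0.9991 at 95.8%.

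**Step 5: how often.** Under the null, the chance of landing in a window equals its width: 0.1% for the nearest pairing, 0.4% for the other. Under HR 0.7306 it is the difference in power between the window's two ends.

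- Nearest pairing: 0.9154 − 0.9127 = 0.27% at alpha 0.024, and 0.9035 − 0.9000 = 0.35% at alpha 0.021.
- Opposite pairing: 0.9127 − 0.9000 = 1.27% and 0.9154 − 0.9035 = 1.19%.

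**The case against.** **The intervals decide nothing.** The log-rank p-value is the primary result, and the Cox model is labelled supportive, with its interval an adjunct. This stands. A reader might infer that the wrong level puts the OS test or its error rate at risk. The documents do not support that, because no decision rule uses the interval.

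**Most of the affected intervals cannot conflict with the test at all.** The Kaplan-Meier medians, percentiles and survival rates are per-arm estimates with no null value of HR = 1. This also stands. Only the Cox hazard-ratio interval can appear to disagree.

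**The 0.021 case is narrow.** It is a tested level only if the interim OS analysis is not performed and rPFS fails. The 0.021 in Section 3.4 belongs to a positive interim, after which final OS is descriptive. On the planned path, with an interim, only 0.024 lacks a level. That limits the reach of the point but does not remove it.

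**Matched levels do not guarantee agreement.** The Cox interval and the log-rank test are different statistics and can differ slightly at the boundary. True; the windows above treat them as exact counterparts, which is an approximation.

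**A blanket 1 − 2α rule would create a new conflict.** After a positive interim with rPFS not met, Section 3.4's nominal alpha of 0.021 would imply 95.8%, whereas footnote 1 in 8.2.2 sets 95%. This is right, and the fix below is restricted accordingly.

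**Conclusion.** The point holds as a minor inconsistency within the SAP. Section 8.2.1 omits the 95.2% and 95.8% levels that match two of its four tested alphas, and it does not say which of its two levels replaces them.

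With the nearest whole percentage, the hazard-ratio interval is off by about 1% in width and can disagree with the test over 0.001 in p. With the opposite pairing, the error is just under 4% and the window is 0.004. These figures assume exactly 508 deaths, 2:1 information and a normal approximation shared by the log-rank test and the Cox interval.

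Type I error, power and the study conclusion are unaffected. It would be wrong to read this as a flaw in the primary OS test; it concerns the level of an adjunct interval.

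**What to change.** In SAP 8.2.1, for the scenarios where final OS is formally tested, replace the two-way choice with a mapping laid out as in the 8.2.2 tables:

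- Interim OS not met, rPFS not met (0.020): 96%.
- Interim OS not performed, rPFS not met (0.021): 95.8%.
- Interim OS not met, rPFS met (0.024): 95.2%.
- Interim OS not performed, rPFS met (0.025): 95%.

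Apply this at least to the Cox hazard ratio. The per-arm Kaplan-Meier intervals may follow it for consistency, but nothing inferential depends on them. State that when interim OS is met, final OS is descriptive and keeps the 95% interval of footnote 1 in 8.2.2. A sentence noting that Cox and log-rank results may differ slightly at the boundary would forestall queries.

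The cost is a short SAP edit and one parameter in the OS tables and figures. No new data or analysis is needed, and the test does not change.
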